6.8.6 Neutropenia

Neutropenia has been observed in patients receiving tarlatamab. The risk mitigation plan includes monitoring of laboratory parameters (including, but not limited to, white blood cell count and absolute neutrophil count) which will be evaluated at baseline and monitored throughout the study. Specific recommendations for the management of neutropenia, and infusion interruption and stopping rules are found in the [Table 6-4](#).

Table 6-4. Tarlatamab Dose Modification Guidelines for Adverse Events

Grade	Interruption/ Delay	Specific Management	Re-start guidance	Permanent Discontinuation
Non-febrile Neutropenia				
3	Interrupt tarlatamab until the event improves to grade ≤ 2	Assess for other potential etiologies of neutropenia, including concomitant medications and underlying infection Consider bone marrow biopsy, anti-neutrophil antibodies Granulocyte colony-stimulating factor (G-CSF) administration permitted	Resume tarlatamab no less than 72 hours after the initial observation of the grade 3 adverse event at the same dose level	Initial grade 3 non-febrile neutropenia does not improve to \leq grade 1 in 3 weeks
4	Interrupt tarlatamab until the event improves to grade ≤ 2	Assess for other potential etiologies of neutropenia, including concomitant medications and underlying infection Consider bone marrow biopsy, anti-neutrophil antibodies Consider G-CSF administration	Resume tarlatamab no less than 72 hours after the initial observation of the grade 4 adverse event and discuss with medical monitor the restarting dose	Initial grade 4 non-febrile neutropenia event lasts > 7 days

G-CSF = granulocyte colony-stimulating factor

7. Discontinuation Criteria

Subjects have the right to withdraw from investigational product and/or **noninvestigational product(s)/auxiliary medicinal product(s)**, protocol procedures, or the study as a whole at any time and for any reason without prejudice to their future medical care by the physician or at the institution.

The investigator and/or sponsor can decide to withdraw a subject(s) from investigational product, device, and/or **noninvestigational product(s)/auxiliary medicinal product(s)**, protocol procedures, or the study as a whole at any time prior to study completion for the reasons listed in Sections [7.1](#), [7.2.1](#), and [7.2.2](#).

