Cytokine Release Syndrome (CRS)	
CRS is a recognized adverse drug reaction of tarlatamab administration due to safety data from tarlatamab phase 1 first in human Study 20160323 for the indication SCLC.
 
CRS is a systemic inflammatory response characterized by a release of cellular cytokines. CRS is risk of T-cell directed therapies. CRS is a risk associated with therapy with the approved BiTE[®] molecule, blinatumomab (anti-CD19 BiTE[®] antibody construct) in patients with acute lymphoblastic leukemia (ALL) and is associated also with other BiTE[®] molecules currently in development for treatment of solid and hematologic cancers.
 
Clinical signs and symptoms of CRS may include the following:
 
 • Constitutional – fever ± rigors, malaise, fatigue, anorexia, myalgias, arthralgias, nausea, vomiting, headache • Skin – rash • Gastrointestinal – nausea, vomiting, diarrhea • Respiratory –dyspnea, tachypnea, hypoxemia • Cardiovascular – tachycardia, widened pulse pressure, hypotension, increased cardiac output (early), potentially diminished cardiac output (late) • coagulation: elevated D-dimer, hypofibrinogenemia ± bleeding • renal: azotemia • hepatic: transaminitis, hyperbilirubinemia 
Infusion reactions may be clinically indistinguishable from manifestations of CRS. .

Neutropenia	
Neutropenia has been observed in patients receiving tarlatamab. The risk mitigation plan includes monitoring of laboratory parameters (including, but not limited, to white blood cell count and absolute neutrophil count) which will be evaluated at baseline and monitored throughout the study. Specific recommendations for the management of neutropenia, and infusion interruption and stopping rules are found in Table 6-4.

ALL = acute lymphoblastic leukemia; BiTE[®] = bispecific T-cell engager; CD19 = cluster of differentiation 19; CRS = cytokine release syndrome; SCLC = small cell lung cancer.

Refer to the tarlatamab Investigator’s Brochure for further description of key safety risks.

A clinical safety monitoring and mitigation strategy with emphasis on cytokine release syndrome, neurological toxicities, and pituitary dysfunction will be implemented in this study which will include but not be limited to prevention, ongoing monitoring, early recognition, and prompt management. Refer to Section 6.8 for detailed management recommendations.

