6.2.1.2.1 Dose Limiting Toxicity

Dose-limiting toxicity (DLT) is defined as any qualifying toxicity that is at least possibly related to tarlatamab with an onset within the first 28 days following first dose with either of the following criteria:

- Grade 3 adverse event lasting more than 3 days (with the exception of fatigue and Grade 3 non-febrile neutropenia that improves to \leq Grade 1 within 3 weeks including the use of growth factor support per neutropenia management guidelines [see Section 6.8.6]);
- \geq Grade 4 adverse event regardless of duration (with the exception of grade 4 non-febrile neutropenia lasting less than or equal to 7 days including the use of growth factor support per neutropenia management guidelines [see Section 6.8.6]).

Laboratory parameters of Grade 4, not considered clinically relevant and improved to Grade \leq 2 within 72 hours, will not be considered DLT's.

Asymptomatic grade 4 electrolyte abnormalities that last $<$ 72 hours, are not clinically complicated, and resolve spontaneously or respond to conventional medical interventions will not be considered DLTs.

The following adverse events will NOT be adjudicated as DLT regardless of the grade or duration:

- Lymphopenia
- Fever
- Tumor lysis syndrome (TLS) including associated manifestations attributable to TLS (eg, electrolyte abnormalities, renal dysfunction, hyperuricemia)

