6.2.2.1.2 Dose Delays

During the first 28 days DLT observation period, if the dosing of tarlatamab is delayed for more than 72 hours for reasons other than DLT during the DLT evaluation period, a replacement subject may be enrolled and assigned to the same dose level. The subject may continue on study only after discussion with the Medical Monitor.

After the 28-day DLT observation period, if the dosing of tarlatamab is delayed for ≤ 2 weeks, the subject should resume the treatment as soon as possible if deemed safe by the investigator. The investigator should inform the Amgen Clinical team as soon as the unexpected dosing interruption occurs. If the dosing of tarlatamab is delayed between 2 to 4 weeks due to severe or life-threatening treatment-related adverse events, the subject can resume treatment if the toxicities resolve to grade ≤ 1 or return to subjects' baseline values within 4 weeks and restarting of therapy has been deemed safe by the investigator and medical monitor.

If the dosing of tarlatamab is delayed for more than 4 weeks due to severe or life-threatening treatment-related adverse events, the subject will be discontinued from investigational product (IP). If the dosing delay occurred under other conditions, the

case will be reviewed by the Sponsor to determine whether and when the subject will be allowed to resume tarlatamab.

For adverse events related to CRS, neurological events, and pituitary dysfunction, please see Sections 6.8.1, 6.8.2, and 6.8.3 respectively for guidelines for dose delays.

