6.2.2.1.3 Rules for Withholding or Restarting

Tarlatamab should be withheld for any of the following:

- DLT
- Symptomatic hypophysitis (See Section 6.8.3)
- Criteria for conditional withholding of tarlatamab due to potential hepatotoxicity (Section 6.2.3)

Tarlatamab dosing can be resumed if the toxicities resolve to grade ≤ 1 or return to subjects' baseline values within 4 weeks. The restarting of therapy should be deemed safe by the investigator and medical monitor.

Subjects should not be restarted with tarlatamab if the following treatment-related adverse events occur:

- Any grade ≥ 4 adverse events except those not considered DLT as described in Section 6.2.1.2.2
- Grade 3 adverse event(s) that do not recover to Grade 0-1 within 4 weeks
- Any grade 3 adverse events that recur (with the exception of grade 3 laboratory parameters not considered clinically relevant or recurrent non-febrile grade 3 neutropenia which resolves with supportive care to grade ≤ 1 or returns to subjects' baseline values within 4 weeks)
- Criteria for permanent withholding of tarlatamab due to potential hepatotoxicity (Section 6.2.3)

For adverse events related to CRS, neurological events and pituitary dysfunction, please see Sections 6.8.1, 6.8.2, and 6.8.3 respectively for guidelines for withholding and restarting criteria to pause enrollment.

At any point during the study, enrollment will be paused at the occurrence of 2 or more Grade 4 or one or more Grade 5 IP related adverse events. DLRT will be reconvened to review the safety data and determine appropriate next step that may include but not limited to implementing safety/toxicity management, informing health authorities, voluntarily putting the clinical trial on hold, or proceeding with enrollment (note: following the occurrence of an enrollment pause and DLRT review, a subsequent enrollment pause will occur at the occurrence of 2 or more new Grade 4 or one or more Grade 5 IP

related adverse events; additionally, if a pause and a DLRT has already occurred and the appropriate safety/toxicity management for Grade 4 adverse events have already been implemented a subsequent enrollment pause may not occur).

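### When a first treatment-related grade 3 non-febrile neutropenia recovers in about week 4, Protocol Table 6-4 requires a permanent stop, but 6.2.2.1.2 (or 6.2.2.1.3, if it was a DLT) permits restart

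*Protocol*

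**What the plan says.** **The drug-specific rule.** The permanent-discontinuation column of Table 6-4 (Protocol 6.8.6) reads, for grade 3, "Initial grade 3 non-febrile neutropenia does not improve to" grade 1 or below in 3 weeks. The same row interrupts dosing until grade 2 or below and allows resumption at the same dose no sooner than 72 hours after the event was first seen. Table 2-1 in Section 2.3 sends the reader there: "Specific recommendations for the management of neutropenia, and infusion interruption and stopping rules are found in Table 6-4". Section 6.8.6 says much the same.

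**The general rules.** Section 6.2.2.1.2 opens its later-delay rules with "After the 28-day DLT observation period". It then says: "If the dosing of tarlatamab is delayed between 2 to 4 weeks due to severe or life-threatening treatment-related adverse events", the subject can resume on recovery to grade 1 or below, or to baseline, within 4 weeks, if the investigator and medical monitor consider it safe. Treatment ends only when such a delay passes 4 weeks. Section 6.2.2.1.3 lists three reasons to withhold: a DLT, symptomatic hypophysitis and hepatotoxicity criteria. It continues: "Tarlatamab dosing can be resumed if the toxicities resolve to grade" 1 or below, or return to baseline, within 4 weeks, and "The restarting of therapy should be deemed safe by the investigator and medical monitor". A separate list there bars restart after related grade 3 events "that do not recover to Grade 0-1 within 4 weeks".

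**The DLT definition.** Section 6.2.1.2.1 exempts grade 3 non-febrile neutropenia that improves to "Grade 1 within 3 weeks including the use of growth factor support per neutropenia management guidelines", citing 6.8.6.

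**The concern.** Two parts of the protocol give different answers for the same subject, and no sentence ranks them. Sections 6.2.2.1.2 and 6.2.2.1.3 each pass CRS, neurological and pituitary events on to 6.8.1, 6.8.2 and 6.8.3, but neither names 6.8.6. A site working from these sections is therefore never sent to the 3-week limit.

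At stake is a patient-safety stopping rule for a risk that Section 2.3 calls identified, applied at approximately 25 sites. On the permissive reading, a subject whom the drug-specific table would stop for good is dosed again. Sites could also differ in whom they discontinue.

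**Working it through.** **1. Which general clause reaches the event.**

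- *Section 6.2.2.1.2* applies to a severe or life-threatening related event that delays dosing by 2 to 4 weeks after the DLT period.
- *Section 6.2.2.1.3, restart sentence* follows a list in which a DLT is the only entry that can describe a neutropenia. Under 6.2.1.2.1 the event is a DLT if it is at least possibly related, starts within 28 days of first dose, lasts more than 3 days at grade 3, and misses the 3-week exemption. Later-onset events are not DLTs, so this sentence does not reach them.

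**2. Outcomes by recovery day.** Neither limit states when its clock starts. Taking both from onset, 3 weeks = 21 days and 4 weeks = 28 days:

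| First at grade 1 or below | Table 6-4 | 6.2.2.1.2, or 6.2.2.1.3 if a DLT |
|---|---|---|
| By day 21 | May continue | Restart permitted |
| Days 22 to 28 | Permanent discontinuation | Restart permitted |
| After day 28 | Permanent discontinuation | No restart |

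Only the middle row conflicts. If the 4 weeks in 6.2.2.1.2 run instead from the missed dose, which under 2-weekly dosing can fall 0 to 14 days after onset, that limit ends on day 28 to 28 + 14 = 42 from onset.

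The baseline alternative adds a second route. Eligibility (criterion 111) admits ANC of 1 x 10^9/L or more. Assuming a count near that floor is grade 2 (the protocol does not reproduce the grading bands), return to baseline satisfies the general rules but not Table 6-4.

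**3. Restart grade.** For delays over 2 weeks, 6.2.2.1.2 asks for grade 1 or below, or baseline, whereas Table 6-4 asks for grade 2 or below. For delays of 2 weeks or less, 6.2.2.1.2 sets no grade, so nothing conflicts there.

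**4. Size.** Section 2.2.2.3 reports treatment-emergent grade 3 neutropenia in 3 of 113 subjects, 112 of them from the SCLC study.

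- Rate: 3/113 = 2.65%. Clopper-Pearson 95% limits are the 0.025 quantile of Beta(3, 111) and the 0.975 quantile of Beta(4, 110): 0.55% and 7.56%.
- In the planned 60 subjects: 60 x 0.02655 = 1.59 grade 3 cases (60 x 0.0055 = 0.33 to 60 x 0.0756 = 4.54).
- Let f be the share of those cases that fall in the conflict window. The documents give no recovery times, so f is assumed. Expected number = 60 x 0.02655 x f; chance of at least one = 1 - (1 - 0.02655f)^60.

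| f | Expected affected | Chance of at least one |
|---|---|---|
| 0 | 0 | 0% |
| 0.10 | 0.16 | 14.7% |
| 0.25 | 0.40 | 32.9% |
| 1 | 1.59 | 80.1% |

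The last line is a bound, and nothing in the documents makes it plausible. Cases that recover within 3 weeks or not by 4 weeks do not count. Nor, for 6.2.2.1.2, do cases already restarted at grade 2 without a delay beyond 2 weeks.

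**The case against.** The strongest reply is that the protocol already settles the matter. Section 6.8.6 and Table 2-1 both place the neutropenia stopping rules in Table 6-4, the DLT definition cites 6.8.6, and an event-specific table is naturally read ahead of general delay rules. A site also cannot take the lenient reading alone, because the medical monitor must agree. On this view only a cross-reference is missing.

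Much of that stands: Table 6-4 is the more natural authority. But the pointers give a location and no ranking. The general sections have a working convention for deferring to Section 6.8, and it omits neutropenia. Section 6.2.2.1.3 also deals with recurrent grade 3 non-febrile neutropenia by name, at 4 weeks, so a reader may think the topic is covered there. Section 7.1 directs adverse-event discontinuations to Table 6-3. Nothing tells the investigator or the medical monitor which limit applies.

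A reader might also infer more than the documents support:

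- *That the 4-week do-not-restart item in 6.2.2.1.3 conflicts with Table 6-4.* It is a prohibition, and a stricter 3-week prohibition simply adds to it.
- *That the restart grades conflict throughout.* They differ for delays over 2 weeks, not for shorter ones.
- *That every recovery slower than 3 weeks is affected.* With both clocks from onset, events unresolved at 4 weeks stop under all the rules.
- *That sites are forced into a breach.* The general rules permit restart and do not require it.

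**Conclusion.** The point holds in a narrow form. The conflict is confined to a first, treatment-related grade 3 non-febrile neutropenia that reaches grade 1 or below, or returns to a grade 2 baseline, between about 3 and 4 weeks. It needs either a 2-to-4-week delay after the DLT period or an event that was a DLT.

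At the observed rate the ceiling is about 1.6 subjects in 60, and the true number may well be zero. That figure assumes the SCLC rate carries over to this population and dose, which the confidence interval does not cover, and it treats every treatment-emergent case as related. Grade 4 events have their own 7-day rule and lie outside this point. No endpoint, sample size or stopping boundary depends on it. It merits correction because it concerns a safety stopping rule and costs very little to put right.

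**What to change.** Add neutropenia (Section 6.8.6, Table 6-4) to the existing cross-reference sentences in 6.2.2.1.2 and 6.2.2.1.3. In each, add a sentence such as: *For an initial grade 3 non-febrile neutropenia, the permanent-discontinuation limit in Table 6-4 governs over the 4-week limit in this section.*

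In the same edit the sponsor should confirm which restart grade applies to delays over 2 weeks: grade 2 or below as in Table 6-4, or grade 1 or below or baseline as in 6.2.2.1.2. Without that, the new cross-reference could loosen the threshold by default. When the 3-week clock starts, and what limit applies to recurrent events, are clinical choices left to the sponsor.

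The cost is a short addition to two sections and one sponsor decision, with no change to design, sample size or analysis.

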7.1 Discontinuation of Study Treatment

Subjects (or a legally acceptable representative) can decline to continue receiving investigational product and/or **noninvestigational product(s)/auxiliary medicinal product(s)** or procedures at any time during the study but continue participation in the study. If this occurs, the investigator is to discuss with the subject the appropriate processes for discontinuation from investigational product or **noninvestigational product(s)/auxiliary medicinal product(s)** and must discuss with the subject the possibilities for continuation of the Schedule of Activities (see Section [1.3](#)) including different options of follow-up (eg, in person, by phone/mail, through family/friends, in correspondence/communication with other treating physicians, from the review of medical records) and collection of data, including endpoints, adverse events, and must document this decision in the subject's medical records. Subjects who have discontinued investigational product and/or **noninvestigational product(s)/auxiliary medicinal product(s)** or procedures should not be automatically removed from the study. Whenever safe and feasible, it is imperative that subjects remain on-study to ensure safety surveillance and/or collection of outcome data.

Subjects may be eligible for continued treatment with Amgen investigational product(s) and/or **noninvestigational product(s)/auxiliary medicinal product(s)** by a separate protocol or as provided for by the local country's regulatory mechanism, based on parameters consistent with Section [11.3](#).

Reasons for early removal from protocol-required investigational product(s) or procedural assessments may include any of the following:

- decision by sponsor
- lost to follow-up

- death
- adverse event (if applicable, refer to [Table 6-3](#))
- subject request
- ineligibility determined
- protocol deviation
- non-compliance
- no longer clinically benefitting (may include clinical deterioration [disease or therapy related] or need for a change in systemic therapy; Scher et al, 2016)
- requirement for alternative therapy

7.2 Discontinuation From the Study

Withdrawal of consent for a study means that the subject does not wish to receive further **investigational product(s), and/or noninvestigational product(s)/auxiliary medicinal product(s)** or procedures, and the subject does not wish to or is unable to continue further study participation. Subject data up to withdrawal of consent will be included in the analysis of the study, and where permitted, publicly available data can be included after withdrawal of consent. The investigator is to discuss with the subject appropriate procedures for withdrawal from the study, and must document the subject's decision to withdraw in the subject's medical records.

If a subject withdraws from the study, he/she may request destruction of any samples taken and not tested, and the investigator must notify Amgen accordingly (see Section [11.6](#) for further details). Refer to the Schedule of Activities (Section [1.3](#)) for data to be collected at the time of study discontinuation and follow-up and for any further evaluations that need to be completed.

7.2.1 Reasons for Removal From Washout Period, Run-in Period, or Invasive Procedures

Not applicable for this study.

7.2.2 Reasons for Removal From Study

Reasons for removal of a subject from the study are:

- Decision by sponsor
- Withdrawal of consent from study
- Death
- Lost to follow-up

7.3 Lost to Follow-up

A subject will be considered lost to follow-up if he or she repeatedly fails to return for scheduled visits and is unable to be contacted by the study site.

The following actions must be taken if a subject fails to return to the clinic for a required study visit:

- The site must attempt to contact the subject and reschedule the missed visit as soon as possible and counsel the subject on the importance of maintaining the assigned visit schedule and ascertain whether or not the subject wishes to and/or is able to continue in the study.
- In cases in which the subject is deemed lost to follow-up, the investigator or designee must make every effort to regain contact with the subject (where possible, 3 telephone calls and, if necessary, a certified letter to the subject's last known mailing address or local equivalent methods). These contact attempts are to be documented in the subject's medical record.
- If the subject continues to be unreachable, he/she will be considered to have withdrawn from the study with a primary reason of lost to follow-up.
- For subjects who are lost to follow-up, the investigator can search publicly available records where permitted to ascertain survival status. This ensures that the data set(s) produced as an outcome of the study is/are as comprehensive as possible.

8. Study Assessments and Procedures

Study procedures and their time points are summarized in the Schedule of Activities (see Section 1.3).

As protocol waivers or exemptions are not allowed if an enrolled subject is subsequently determined to be ineligible for the study, this must be discussed with the sponsor immediately upon occurrence or awareness to determine if the subject is to continue or discontinue study treatment.

Adherence to the study design requirements, including those specified in the Schedule of Activities, is essential and required for study conduct.

8.1 General Study Periods

8.1.1 Screening and Enrollment

Informed consent must be obtained before completing any screening procedure or discontinuation of standard therapy for any disallowed therapy. After the subject or legally authorized representative has signed the ICF, the site will register the subject and screen the subject in order to assess eligibility for participation. The screening window is up to 28 days.

All screening evaluations must be completed and reviewed to confirm that potential subjects meet all eligibility criteria. The investigator will maintain a screening log to record details of all subjects screened and to confirm eligibility or record reasons for screening failure, (see Section 5.4) as applicable.

If a subject has not met all eligibility criteria at the end of the screening period, the subject will be registered as a screen fail. Screen fail subjects may be eligible for re-screening 1 time.

Rescreen subjects must first be registered as screen failures and subsequently registered as rescreeens. Once the subject is registered as rescreened, a new 28-day screening window will begin. Subjects will retain the same subject identification number assigned at the original screening. If the rescreening period begins more than 28 days after the original signing of the ICF, all screening procedures, including informed consent, must be repeated.

